## 6.6 Review and Documentation of Medications and Supplements

All medications or supplements subjects are taking or have taken within 30 days prior to Visit 1 through Visit 9 will be recorded in the subject's medical record and the eCRF.

All medications and supplements (other than IMP) taken by the subject after Visit 1 through Visit 8 assessments will be considered "concomitant" medications and supplements.

Medications and supplements taken prior to Visit 1 that are no longer being taken at Visit 1 will be considered "prior" medications and supplements.

Medications and supplements should be recorded according to the generic name when possible. The use of concomitant medications and supplements should be limited to those that are medically necessary. Any medication or supplement used should have an indication recorded, and for concomitant medications and supplements, this indication must be represented as either for the treatment of an AE, for the management of a pre-existing condition, or for prophylaxis.

Dosage increases for any concomitant medication or supplement should be noted and the reason for the dosage increase recorded as an AE (assumes worsening condition). The side effects of concomitant medications will be recorded as AEs.

Any subject whose condition becomes disqualifying during the course of the study may be treated for that condition. If the condition is suspected during Screening, the subject should not be enrolled. Treatment of the condition should be instituted according to the Investigator's/attending physician's judgment.

Medications that have no treatment intent but rather are part of supportive routine care such as local anesthetics, intravenous solutions to maintain fluid balance and keep access open, medications used for prophylaxis, and narcotics for postsurgical pain must also be recorded in the subject's medical record and eCRF.

## 7 ADVERSE EVENTS AND SAFETY REPORTING

Information about all adverse events, whether volunteered by the patient, discovered by Investigator questioning, or detected through physical examination, laboratory test or other means, will be collected and recorded on the Adverse Event Case Report Form and followed-up as appropriate.

Medical conditions present at study entry are considered pre-existing conditions and will be documented as medical history in the study source and eCRF documents. All adverse events, including worsening of pre-existing conditions, must be reported and documented as described below.

### 7.1 Safety and Tolerability Assessments

Volunteered, observed, and elicited reports of adverse events must be recorded. This includes adverse events the patient reports spontaneously, those the Investigator observes, and those the study staff elicits in response to open-ended questions during study visits.

Each adverse event will be assessed by the Investigator with regard to seriousness, severity, and relatedness to the study treatment for recording in the eCRF.

### 7.2 Definition of Adverse Event

An adverse event is any untoward medical event that occurs in a patient or patient administered a pharmaceutical product and that does not necessarily have a causal relationship with this treatment. An adverse event can therefore be any unfavorable and unintended sign (including abnormal laboratory findings), symptom, or disease temporally associated with the use of a medicinal (investigational) product, whether or not related to the medicinal (investigational) product.

### 7.3 Adverse Events of Special Interest

#### 7.3.1 Adverse Events of Hypoglycemia

The CTCAE (version 5.0) criteria for mild, moderate, and severe hypoglycemia based on blood glucose will be used, as shown below:

Mild: < 70 – 55 mg/dL (< 3.8 - 3.0 mmol/L)

Moderate: < 55 – 40 mg/dL (< 3.0 - 2.2 mmol/L)

Severe: < 40 – 30 mg/dL (< 2.2 - 1.7 mmol/L)

Life Threatening: < 30 mg/dL (< 1.7 mmol/L)

### 7.4 Definition of Serious Adverse Event

International Conference on Harmonization (ICH) Guidelines define a serious adverse event (SAE) as any untoward medical occurrence that:

- Results in death.
- Is life-threatening.

- Requires or prolongs existing hospitalization.
- Results in persistent or significant disability or incapacity.
- Is a congenital anomaly or birth defect.
- Important medical events that may not result in death, be life-threatening or require hospitalization, but that may jeopardize the patient or require medical intervention to prevent one of the above outcomes, should also be considered serious when based upon the Investigator's medical judgment.

Events not to be reported as SAEs are the following:

- Routine treatment or monitoring of the studied indication, not associated with any deterioration in condition.
- Treatment, including hospitalization, which was elective or pre-planned for a pre-existing condition that is unrelated to the indication under study and did not worsen.
- Treatment on an emergency, outpatient basis for an event not fulfilling any of the aforementioned definitions of "serious" and not resulting in hospital admission.

## 7.5 Recording Adverse Events

All adverse events experienced during the trial, regardless of relationship to study medication, must be recorded on the Adverse Event eCRF from the time of patient consent until completion of patients End-of-Study Visit (Visit 9). All serious adverse events will be collected through Visit 9. The Investigator must continue to follow all non-serious events possibly related to the study medication and all serious adverse events until they resolve or until the Investigator assesses them in writing as chronic or stable.

Regardless of relationship to study medication, the event must be recorded on the Adverse Event eCRF. Adverse event documentation should include the following information:

- Standard medical terminology for the AE
- Description of adverse event
- Date and time of onset
- Date and time of resolution of the adverse event
- Whether or not the event is ongoing
- Severity of the event
- Relationship between the adverse event and the investigational product
- Description of any actions taken (e.g., medications, treatments)
- Outcome of the AE
- Whether or not the effect was serious and/or unanticipated

Whenever possible, a diagnosis should be given when signs and symptoms are due to common etiology (e.g., cough, runny nose, sneezing, sore throat, and head congestion should be reported as "upper respiratory infection"). For the purposes of this study, hypoglycemic events will be considered adverse events and should be recorded in source and eCRF records.

When a diagnosis is not available, each adverse event should be reported separately. For example, "nausea and vomiting" should be split into two separate events.

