Subjects will then undergo a Treatment Phase consisting of a treatment period of 12 weeks that will start at Visit 3 (Week 0) and outpatient visits at Weeks 1, 2, 4, 8, and 12 (final visit). At each visit, concomitant medication will be reviewed, weight will be measured, and sufficient quantity of medication will be dispensed to last until the next nominal clinic visit. Medication compliance check will be performed, self-monitored fasting morning blood glucose (finger-stick) will be recorded 3 days weekly in the morning and subjects' diaries will be reviewed. Vital signs (SBP/DBP, heart rate and oral temperature) will be recorded. Adverse events will be monitored and recorded. ORMD-0801 morning treatment will be administered in clinic during Visits 3, 6 and 7.

At Visit 3, urine pregnancy test will be performed for females of childbearing potential. At Visit 8, subjects will have HbA1c evaluations and MRI-PDFF performed. At Visits 3 and 8, a complete physical exam and CAP-Fibroscan will be performed.

At Visits 3 (baseline), 6, 7, and 8, patients will have clinical laboratory evaluations (serum chemistry, hematology) and blood lipids performed. Fasting blood glucose, insulin (also used for HOMA estimates) and adiponectin levels will be measured.

The End-of-Study (EOS) Visit (Visit 9) will be conducted 4 weeks following the last scheduled treatment visit. Subjects concomitant medications will be reviewed, and weight will be measured. A complete physical exam and ECG will be performed and vital signs (SBP/DBP, heart rate and oral temperature) will be measured if deemed necessary by the investigator. Clinical laboratory evaluations [serum chemistry (including liver function tests (LFTs) and blood lipids) and hematology] will be performed. Fasting blood glucose, fasting insulin, HbA1c and adiponectin levels will be measured. Subject diaries will be collected and reviewed for self-monitored fasting morning blood glucose. Adverse events will be monitored and recorded. Subjects who are discontinued early from the study will complete the EOS evaluations at the time of early discontinuation.

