### **3.5 End-of-Study (EOS) Phase (Visit 9, Week 16, Days 112±4)/Early Termination**

The EOS Visit (Visit 9) will be conducted 4 weeks following the last scheduled treatment Visit. Subjects will report to the clinic in the morning following a 10-hour fast. The following procedures will be performed:

- Review of concomitant medication;
- Complete PE, only if the investigator deems it necessary;
- Measurement of weight;
- Collection of unused ORMD-0801 medication;
- 12-Lead ECG, only if the investigator deems it necessary;
- Measurement of vital signs (SBP/DBP, heart rate and oral temperature), only if the investigator deems it necessary;
- Fasted blood samples will be collected for clinical laboratory evaluations (see [Section 6.5.5.1](#) for a complete list of tests performed):
  - Serum Chemistry including liver function tests (LFTs) and blood lipids;
  - Hematology;
- Measurement of fasting blood glucose and fasting insulin for HOMA estimates;
- Review/Collect subject diaries for self-monitored fasting morning blood glucose;
- HbA1c;
- Adiponectin test;
- AEs/SAEs assessment.

Patients who are discontinued early from the study will complete the EOS evaluations at the time of early discontinuation.

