**Table 1: Daily Schedule of Events from Screening Visit 1 through End-of-Study Visit 9**

Assessments	Screening	Placebo	Treatment						Unscheduled Visit	End-of-Study/ Early Termination
			0	1	2	4	8	12		
Week	up to -6	-2	0	1	2	4	8	12	Not Defined	16
Days	Up to -42	-14	0±4	7±4	14±4	28±4	56±4	84±4		112±4
Visit	1	2	3	4	5	6	7	8	Unscheduled	9
Written informed consent	X									
Inclusion/Exclusion	X									
Medical and social history (including tobacco, alcohol, caffeine, and drug use)	X									
Prior and Concomitant Medication 	X	X	X	X	X	X	X	X		X
Demographics (sex, age, race and ethnicity)	X									
Complete physical examination	X		X					X		(X  )
Height, Weight and BMI 	X	X	X	X	X	X	X	X		X
Pregnancy Test 	X	X	X							
Treatment Administration 		X 	X 	X	X	X 	X 			
Dispense/Collect Medication 		X	X	X	X	X	X	X		X
Medication compliance check			X	X	X	X	X	X		
ECG	X									(X  )

Assessments	Screening	Placebo	Treatment						Unscheduled Visit	End-of-Study/ Early Termination
			0	1	2	4	8	12		
Week	up to -6	-2	0	1	2	4	8	12	Not Defined	16
Days	Up to -42	-14	0±4	7±4	14±4	28±4	56±4	84±4		112±4
Visit	1	2	3	4	5	6	7	8	Unscheduled	9
Vital signs 	X	X	X	X	X	X	X	X		(X  )
Clinical laboratory evaluations 	X		X			X	X	X	(X  )	X
Fasting blood glucose and fasting Insulin 		X	X			X	X	X	(X  )	X
Self-monitored fasting morning blood glucose 		X	X	X	X	X	X	X		
Dispense Diary/ Review Diary Data		X	X	X	X	X	X	X		X
Adiponectin Test			X			X	X	X		X
HbA1c	X							X		X
Blood lipids: Total cholesterol, LDL, HDL, Triglycerides	X		X			X	X	X		X
CAP-Fibroscan	X		X					X		
MRI-PDFP	X							X		
Viral serology 	X									
TSH and FSH 	X									
AE/SAE assessment 	X	X	X	X	X	X	X	X	X	X

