-  Screening labs will include standard hematology, fasting serum chemistry, plus TSH. FSH will also be performed for women who are post-menopausal, if results are not available.
-  Adverse events will be collected throughout the study beginning from the time the patient signs the consent form until the EOS (Visit 9) evaluations.

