If either of the criteria listed below is met, enrollment of new subjects and dosing of ongoing subjects will be temporarily stopped. The Investigator, Sponsor, and the Medical Monitor will discuss whether a lower dose or any additional treatment guidelines should be implemented, or if the trial should be permanently stopped. Any proposed changes to the protocol to address such findings will be submitted for review and approval by the IRB and U.S. Food and Drug Administration (FDA) prior to re-starting the trial.

1. A death within 30 days after IMP administration where there is a reasonable possibility that the drug caused the event;
2. Two Grade 4 AEs where there is a reasonable possibility that the IMP caused the events.

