#### 7.5.2.1 Pregnancy Reporting

If the subject or partner of a subject participating in the study becomes pregnant during the study or within 30 days of discontinuing study medication, the Investigator should report the pregnancy to Oramed within 24 hours of being notified. The Exposure In-Utero form to the Investigator for completion.

The subject or partner should be followed by the Investigator until completion of the pregnancy. If the pregnancy ends for any reason before the anticipated date, the Investigator should notify the Sponsor. At the completion of the pregnancy, the investigator will document the outcome of the pregnancy. If the outcome of the pregnancy meets the criteria for immediate classification as an SAE (i.e., postpartum complication, spontaneous abortion, stillbirth, neonatal death, or congenital anomaly), the Investigator should follow the procedures for reporting an SAE.

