## 7.9 Assessment of Adverse Event Outcome

Outcome of AEs will be defined according to ICH Topic E2B, ICH Guideline.

- **Recovered/Resolved:** The subject has recovered fully from the AE without any remaining effects or impairment.
- **Recovered/Resolved with Sequelae:** The subject has recovered, but with an after effect possibly due to disease or treatment.
- **Not Recovered/Not Resolved:** The condition is still present.
- **Fatal:** Fatal should only be used when death is possibly related to the AE.
- **Unknown:** The primary outcome is not known at the time of the final assessment. If an outcome for an AE is not available at the time of the initial report, follow-up will proceed until an outcome is known or followed up to the Final Study Visit. Any subject with a possible IMP-related AE at the Final Study Visit will be followed until resolution or stabilization of the event. Further, any SAE, whether or not related to IMP (active or Placebo), that occurs within 30 days following the last dose of IMP will be followed until resolution or stabilization of the event.

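### No safety contact is scheduled after an early-termination visit, so a dosed subject who withdraws without an open event has little or no scheduled post-dose AE/SAE ascertainment

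*Combined protocol and SAP*

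**What the plan says.** **Collection window.** Section 7.5 states that adverse events "must be recorded on the Adverse Event eCRF from the time of patient consent until completion of patients End-of-Study Visit (Visit 9"), and gives SAE collection the same end. Footnote 13 to Table 1 agrees: "Adverse events will be collected throughout the study beginning from the time the patient signs the consent form until the EOS (Visit 9) evaluations".

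**When that visit happens.** For completers, section 3.5 places Visit 9 four weeks after the last scheduled treatment visit. For others, it says: "Patients who are discontinued early from the study will complete the EOS evaluations at the time of early discontinuation". Section 3.1 says the same. Table 1 has a single last column, "End-of-Study/ Early Termination", with no later visit or call.

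**Provisions that look 30 days past dosing.**
- Section 4.3, first criterion for pausing enrollment and dosing: "A death within 30 days after IMP administration where there is a reasonable possibility that the drug caused the event".
- Section 7.5.2.1, pregnancies to be reported: the subject or a partner "becomes pregnant during the study or within 30 days of discontinuing study medication".
- Section 7.9, any SAE that "occurs within 30 days following the last dose of IMP will be followed until resolution or stabilization of the event".

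**Who stays in the analysis.** Under section 4.3, all randomized and treated subjects enter the safety analyses, and treated subjects who are withdrawn are not replaced. Under section 3.7, subjects taken off study drug by the glucose rules remain on the visit schedule (if possible, in the case of the high-glucose rule).

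**The concern.** Read together, these sections end scheduled safety collection at the early-termination visit. No single sentence says so, but nothing in the schedule says otherwise. A subject who takes capsules until leaving the study may have the last AE/SAE assessment on, or shortly after, the last dosing day. A completer is seen again about four weeks after treatment ends.

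This matters because safety is the primary objective and endpoint. Withdrawn subjects stay in the safety population, are not replaced, and are the ones observed for the shortest time after dosing. The definition of a treatment-emergent event in section 8.2.1 has no end date, so a late event would count if it were known. The limit lies in collection, not in the analysis rule.

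The sponsor chose a 30-day horizon in three places. For a subject who has left without an open event, no scheduled contact would show whether anything happened within it. The last scheduled pregnancy test is at Visit 3 (section 6.5.8, Table 1), so a pregnancy after withdrawal would also surface only if someone reported it.

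**Working it through.** **1. Completers: reproduce the stated interval.** Visit 8 is Day 84 ± 4 and Visit 9 is Day 112 ± 4 (sections 3.4.6 and 3.5, Table 1).
- Nominal: 112 − 84 = 28 days = 4 weeks, as section 3.5 states.
- Shortest: (112 − 4) − (84 + 4) = 108 − 88 = 20 days.
- Longest: (112 + 4) − (84 − 4) = 116 − 80 = 36 days.
- If the last dose is taken the evening before Visit 8 (an assumption), each figure rises by one day: 29, with a range of 21 to 37.

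**2. Early withdrawals.** Let g be the number of days from the last dose to the early-termination visit. Scheduled post-dose coverage is g days, and the uncovered part of a 30-day horizon is 30 − g. The protocol gives no value for g. Section 4.3 asks only for reasonable efforts to bring the subject back. With assumed values:

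| g (assumed) | Covered days | Uncovered days of 30 |
|---|---|---|
| 0 | 0 | 30 − 0 = 30 |
| 7 | 7 | 30 − 7 = 23 |
| 14 | 14 | 30 − 14 = 16 |

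**3. How many subjects.** Section 8.1 plans up to 36 randomized and approximately 30 completing, so 36 − 30 = about 6 non-completers (6/36 = 16.7%). The affected group is smaller if some of the 6 leave with an event already being followed, leave between Visits 8 and 9 when already off drug, or stop drug but keep attending.

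**4. Does anything else schedule a contact?** Each remaining provision, with what sets it in motion:
- Section 3.6, unscheduled visit: investigator discretion.
- Section 4.3, every effort to contact: a missed follow-up appointment or contact. None is scheduled after early termination, so none can be missed.
- Section 4.3, follow-up after withdrawal for a suspected drug-related AE, or after a pregnancy: an event already known.
- Sections 7.5 and 7.9, follow-up to resolution or stabilization: an event already identified.
- Section 7.10: a significant clinical finding at Visit 9.
- Section 7.5.2 and its investigator reporting procedures, and section 7.5.2.1: the site being told of, or knowing of, an SAE or a pregnancy.

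None of these prompts the site to ask a withdrawn subject with no open event how he or she has been since leaving.

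**The case against.** **There is no contradiction.** A reader might infer that the three 30-day provisions conflict with a collection window ending at Visit 9. The documents do not support that. Section 4.3 gives a halting trigger that counts from drug administration, section 7.5.2.1 is a notification rule, and section 7.9 says how long an SAE is followed. All three can operate alongside collection to Visit 9. What remains is that, for these subjects, they depend on volunteered information.

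**Safeguards exist.** The early-termination visit includes an AE/SAE assessment, chemistry with liver tests, hematology, glucose and insulin. A withdrawal who fails to return for it falls under the every-effort rule of section 4.3, whose stated purpose is to confirm satisfactory health. SAE notification within 24 hours has no stated end date. All of this stands and narrows the point to new events after the visit that nobody reports.

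**No late risk is shown.** The only reaction the protocol attributes to ORMD-0801 is hypoglycemia with its symptoms (sections 3.7 and 7.6.1), and the low-glucose rule in section 3.7 looks 12 hours after dosing. This objection stands in full: the protocol offers no evidence that events in the month after dosing are likely.

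**The study is small and descriptive.** It is exploratory and unpowered (section 8.1), with no inferential AE comparison (section 8.2.1). That limits the weight of the point. It does not remove it, because description of safety is the primary purpose.

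**Completers can fall short of 30 days too.** Also correct. The nominal shortfall is 30 − 28 = 2 days, or 30 − 29 = 1, but with the visit windows it can reach 30 − 20 = 10.

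**Conclusion.** The gap is real and narrow. As the sections are written, a dosed subject who withdraws from the study without an open event has scheduled post-dose ascertainment only from the last dose to the early-termination visit, possibly zero days, against a nominal 28 days (20 to 36) for completers. It affects at most about 6 subjects on the planning figure, and probably fewer. Subjects who stop drug but remain in the study are outside it. The conclusion rests on reading the collection window, the timing of the early-termination visit and Table 1 together. The size per subject rests on a delay that the protocol does not give.

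Two larger readings are tempting and should not be drawn:
- **Subject-days.** A reader might multiply 6 × 30 = 180 and treat that as lost safety observation. It assumes that all 6 withdraw while dosing, with no open event and no delay before the visit. No event rate in the documents turns it into expected missed events.
- **Incidence.** A reader might note that one missed event moves an arm's incidence by 1/24 = 4.2 or 1/12 = 8.3 percentage points (36 split 2:1). That is true of any missed event in arms of this size and does not measure this gap.

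I would class this as a cheap improvement to ascertainment of the primary endpoint. It is not an inconsistency, and there is no demonstrated bias.

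**What to change.** In section 7.5, with matching text in section 3.5, Table 1 and footnote 13 (and the parallel sentence in section 3.1):

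1. For subjects who have received study drug and withdraw from the study early, state that AE/SAE and pregnancy collection continues to 30 days after the last dose. Add one telephone contact at about day 30 when the early-termination visit falls materially earlier and the subject has not refused contact. Show the call in Table 1.
2. For all subjects, including completers whose Visit 9 falls before day 30, state that an SAE or pregnancy the site learns of within 30 days of the last dose is recorded. No call is needed for completers, who are already seen 20 to 36 days after Visit 8.

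The 30 days is the documents' own horizon. The change concerns data collection only and leaves dosing, rescue and halting rules as they are.

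Cost: protocol wording and about one short call per early withdrawal, so around 6 on the planning figure and possibly more if attrition is higher. There is no added visit or test. Subjects who refuse contact remain uncovered.
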